10.1.3 Decitabine

Decitabine will be given starting at dose level 1, which is the standard dose and schedule currently in use: 20 mg/m²/day for 5 consecutive days following standard of care guidelines (50).

Decitabine will be given at 20 mg/m²/day, intravenously, over 1 hour on days 1-5 followed by 23 days without decitabine at the discretion of the treating physician per their standard practice. Delays in dosing are allowed per standard institutional practice. Decitabine should be given Days 1-5 unless a delay is deemed necessary by the treating physician for patient safety. If required, dose de-escalation of decitabine to 15 mg/m² is provided for during the safety portion of the study.

Table 5 Dose Levels

Dose Level	CDX-1401/Poly-ICLC	Decitabine	Nivolumab
1	1mg/1.8mg	20mg/m ² days 1-5	3mg/kg days 1,15
-1	1mg/1.8mg	15mg/m ² days 1-5	3mg/kg days 1,15

There will be no dose modifications to the decitabine dose during the first 8 cycles of treatment. After cycle 8, dose reductions may be made at the discretion of the treating physician per their standard practice, but cycles should be given every 4 weeks unless a delay is deemed necessary by the treating physician for patient safety.

Delays in dosing up to 6 weeks are acceptable if deemed necessary for patient safety. Grade 4 neutropenia, transfusion dependence for platelets and red blood cells and the possibility of hospitalization for infections are expected toxicities of the underlying disease process and of standard treatment with decitabine.

Please see below for a detailed study calendar:

PROTOCOL TITLE: I 49217 - Phase 1 CDX-1401/ Poly-ICLC +Decitabine +Nivolumab in Patients with MDS or Low Blast Count AML

Treatment Plan: Cycle 1

Cycle 1														
Day	-14	1	2	3	4	5	6	7	8	...	15	...	28
CDX-1410	X											X		
Poly ICLC	X											X		
Decitabine (DAC)			X	X	X	X	X							
Nivolumab (NIVO)			X									X		

Treatment Plan: Cycles 2-4

Cycles 2-4														
Day	1	2	3	4	5	6	7	8	9	10	...	15	...	28
CDX-1410												X		
Poly ICLC												X		
Decitabine (DAC)	X	X	X	X	X									
Nivolumab (NIVO)	X											X		

PROTOCOL TITLE: I 49217 - Phase 1 CDX-1401/ Poly-ICLC +Decitabine +Nivolumab in Patients with MDS or Low Blast Count AML

Treatment Plan: Non-Vaccine Cycles:

Cycles 5-7, 9-11, 13-15, 17-19, 21-23, 25...														
Day	1	2	3	4	5	6	7	8	9	10	...	15	...	28
CDX-1410														
Poly ICLC														
Decitabine (DAC)	X	X	X	X	X									
Nivolumab (NIVO)	X													

Treatment Plan: Vaccine Booster Cycles:

Cycles 8, 12, 16, 20, 24...														
Day	1	2	3	4	5	6	7	8	9	10	...	15	...	28
CDX-1410	X													
Poly ICLC	X													
Decitabine (DAC)	X	X	X	X	X									
Nivolumab (NIVO)	X													

Treatment is intended for an outpatient setting. However, at the investigator's/physician's discretion, the participant may receive treatment as an inpatient, if deemed necessary.

10.2 Treatment Protocol for the Expansion Cohort

Decitabine is dosed at the MAD determined in the safety portion of the study for 5 days/28 day cycle (Day 1-Day 5 of each cycle per standard of care).

- After cycle 8, dose reductions of decitabine are permitted at the discretion of the treating investigator per the standard of care.

The vaccine is comprised of CDX-1401 (1 mg) given intracutaneously with 1.8 mg of Poly-ICLC. The first dose of the vaccine is given on Day -14 and then, on Day 15 of each decitabine cycle for

PROTOCOL TITLE: I 49217 - Phase 1 CDX-1401/ Poly-ICLC +Decitabine +Nivolumab in Patients with MDS or Low Blast Count AML

the first 4 cycles (total of 5 vaccines). Thereafter, patients will receive a booster vaccine on Day 1 of every 4th cycle, indefinitely.

Nivolumab is to be given at a fixed dose of 3 mg/kg every 2 weeks starting on Day 1 of Cycle 1. For cycles 5 and above, nivolumab is given at a fixed dose of 480mg every 4 weeks on day 1 of every cycle and may continue on protocol until disease progression or the patient elects to discontinue nivolumab.

Decitabine/nivolumab cycles will be given on schedule every 4 weeks unless a delay is deemed clinically necessary by the treating physician/investigator. If the patient requires a delay of more than 6 weeks, they will come off study.

10.3 Definition of Dose-Limiting Toxicity

Dose limiting toxicities (DLTs) are defined as any non-hematologic grade 4/5 toxicities that are definitely, probably, or possibly related to the administration of the investigational agent(s) (see Appendix H for organ specific auto-immune grading of toxicity).

All AEs will be graded according to the NCI-CTCAE scale Version 4.0.

Hematological toxicities are expected in patients with MDS undergoing therapy with decitabine and will not be considered dose limiting. Hematological toxicities will not be deemed dose limiting, in agreement with other studies in patients with MDS and AML.

The initial DLT period will be defined as 28 days after the first dose of decitabine. Given that toxicities related to checkpoint inhibitors may not be immediately manifested, after the first 3 patients have been enrolled, accrual to the expansion cohort will be delayed to monitor for late developing toxicities until all patients in the first 3 patient cohort have been followed until cycle 4 day 29 of decitabine.

Patients will be monitored throughout the study and according to the schedule of procedures and observations. Any auto-immune related events which occur between days 29 and the end of study may be sufficient to interrupt the nivolumab therapy if they are grade 4 or 5 as described below. Patients may be withdrawn from study even if DLT is due to decitabine alone.

Safety monitoring will include careful assessment and appropriate reporting of adverse events, as well as the construction and implementation of a data and safety-monitoring plan (Auditing, Monitoring and Inspecting). Medical monitoring will include a regular assessment of the number and type of serious adverse events. As this is a phase I study, all AEs will be reviewed by the Early Phase Clinical Trials committee at RPCI on a weekly basis.

Management and dose modifications associated with the above AEs are outlined in Section 10.3 and Appendix H.

10.4 Dose Modifications and Treatment Delays

10.4.1 Vaccine

There will be no dose modifications to the doses of CDX-1401 or poly ICLC.

PROTOCOL TITLE: I 49217 - Phase 1 CDX-1401/ Poly-ICLC +Decitabine +Nivolumab in Patients with MDS or Low Blast Count AML

10.4.2 Decitabine

If a dose limiting toxicity is observed with combination therapy, decitabine may be dose reduced to 15mg/m² per the safety lead in. Following the establishment of our MAD, there will be no dose reductions of decitabine in the first 8 cycles of therapy. After Cycle 8, in patients with <5% bone marrow blasts, dose reductions of decitabine are at the discretion of the investigator per the following table. Dose reductions will be recorded for informational purposes only.

Table 6 Acceptable Dose Reductions of Decitabine after Cycle 8

SOC Dose Reduction Schedule	Decitabine
1	20 mg/m ² /day for 5 days
25% dose reduction	15 mg/m ² /day for 5 days
50% dose reduction	10 mg/m ² /day for 5 days

10.4.3 Nivolumab

In the event that a patient experiences a Grade 4 treatment related toxicity due to nivolumab, myocarditis of any grade or intolerable Grade 2 or 3 toxicity, felt to be associated with Nivolumab alone, despite optimal supportive care, treatment with Nivolumab should be permanently discontinued. Refer to **Table 7** for recommended nivolumab dose modifications. If toxicities have resolved to <grade 1, nivolumab may be reintroduced following a period of holding.

Table 7 Nivolumab Dose Modifications and Dosing Delays

Adverse Reaction	Severity	Dose Modification
Myocarditis	Any grade	Permanently discontinue
Colitis	Grade 2 diarrhea or colitis	Withhold dose ^a
	Grade 3 diarrhea or colitis:	
	• Single-agent Nivolumab	Permanently discontinue
Pneumonitis	Grade 4 diarrhea or colitis	Permanently discontinue
	Grade 2 pneumonitis	Withhold dose ^a
Hepatitis	Grade 3 pneumonitis	Permanently discontinue
	Aspartate aminotransferase (AST)/or alanine aminotransferase (ALT) more than 3 and up to 5 times the upper limit of normal or total bilirubin more than 1.5 and up to 3 times the upper limit of normal	Withhold dose ^a
	AST or ALT more than 5 times the upper limit of normal or total bilirubin more than 3 times the upper limit of normal	Permanently discontinue
Hypophysitis	Grade 2 or Grade 3 hypophysitis	Withhold dose ^a
	Grade 4 hypophysitis	Permanently discontinue
Adrenal Insufficiency	Grade 2 adrenal insufficiency	Withhold dose ^a

PROTOCOL TITLE: I 49217 - Phase 1 CDX-1401/ Poly-ICLC +Decitabine +Nivolumab in Patients with MDS or Low Blast Count AML

Adverse Reaction	Severity	Dose Modification
	Grade 3 or 4 adrenal insufficiency	Permanently discontinue
Type 1 Diabetes Mellitus	Grade 3 hyperglycemia	Withhold dose ^a
	Grade 4 hyperglycemia	Permanently discontinue
Nephritis and Renal Dysfunction	Serum creatinine more than 1.5 and up to 2 times the upper limit of normal	Withhold dose ^a
	Serum creatinine more than 2 times the upper limit of normal	Permanently discontinue
Rash	Grade 3 rash	Withhold dose ^a
	Grade 4 rash	Permanently discontinue
Encephalitis	New-onset moderate or severe neurologic signs or symptoms	Withhold dose ^a
	Immune-mediated encephalitis	Permanently discontinue
Other	Other Grade 3 adverse reactions:	
	• First occurrence	Withhold dose ^a
	• Recurrence of same Grade 3 adverse reactions	Permanently discontinue
	• Life threatening or Grade 4 adverse reaction	Permanently discontinue
	• Requirement for 10 mg per day or greater prednisone or equivalent for more than 12 weeks	Permanently discontinue
• Persistent Grade 2 or 3 adverse reactions lasting 12 weeks or longer	Permanently discontinue	

^a: withhold dose and resume nivolumab with the next cycle if resolution of toxicity to ≤ Grade 1.

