10.1 Dosing and Administration

The vaccine is comprised of CDX-1401 (1 mg) given intracutaneously with 1.8 mg of Poly-ICLC. The first dose of the vaccine is given on Day -14 and then, on Day 15 of each decitabine cycle for the first 4 cycles (total of 5 vaccines). Thereafter, patients will receive a booster vaccine on Day 1 of every 4th cycle, indefinitely.

Nivolumab is to be given at a fixed dose of 3 mg/kg every 2 weeks starting on Day 1 of Cycle 1 through cycle 4 day 15. After cycle 5 nivolumab will be given as a flat dose of 480mg every 4 weeks on day 1 of each decitabine cycle (+/-7 day window). Nivolumab administration may continue on protocol until disease progression or the patient elects to discontinue nivolumab.

Decitabine/nivolumab cycles will be given on schedule every 4 weeks unless a delay is deemed clinically necessary by the treating physician/investigator. If the patient requires a delay of more than 6 weeks, they will come off study. The study schema is depicted in **Figure 3**.

Figure 3: Study Schema

For the purposes of this study, 1 cycle = 28 days and is comprised of 5 doses of IV decitabine (days 1-5), 2 doses of nivolumab during cycles 1-4 and 1 dose of nivolumab cycles 5 and above (day 1 and day 15 during cycles 1-4 or day 1 cycles 5 and above) and 1 vaccination (day 15). Protocol therapy may be given at the discretion of the treating physician within a +/-7 day window to accommodate patient’s preference, clinical judgement and schedule or outside this window after discussion with the PI.

Note: When nivolumab and decitabine are administered on the same day, decitabine is administered first, followed by nivolumab.

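### Section 10.4.3 gives two different recovery grades for restarting held nivolumab, and 10.1 and 10.2 do not say whether a nivolumab-only hold counts towards the 6-week off-study limit

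*Combined protocol and SAP*

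**What the plan says.** **Recovery grade.** The body text of section 10.4.3 (Nivolumab) reads "If toxicities have resolved to <grade 1, nivolumab may be reintroduced following a period of holding". Table 7 in that section lists ten situations in which a dose is withheld, and each carries footnote a: "withhold dose and resume nivolumab with the next cycle if resolution of toxicity to ≤ Grade 1".

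**Length of a hold.** Section 10.1 says "Decitabine/nivolumab cycles will be given on schedule every 4 weeks unless a delay is deemed clinically necessary by the treating physician/investigator" and then "If the patient requires a delay of more than 6 weeks, they will come off study". Section 10.2 repeats both statements for the expansion cohort. Section 10.1.3, on decitabine, adds "Delays in dosing up to 6 weeks are acceptable if deemed necessary for patient safety". Under its Other heading, Table 7 makes discontinuation of nivolumab permanent in two time-based cases: "Persistent Grade 2 or 3 adverse reactions lasting 12 weeks or longer" and "Requirement for 10 mg per day or greater prednisone or equivalent for more than 12 weeks".

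**The concern.** Two instructions in one section set different conditions for the same decision. A site that reads the body text requires full resolution before rechallenge; a site that reads the footnote restarts with mild toxicity still present. The decision to re-expose a patient to a checkpoint inhibitor, and the exposure and toxicity then recorded, would depend on which line was read. Section 19.2 describes adverse event rates as part of the primary safety objective, so the post-rechallenge part of that description would mix two rules. The conflict is also a patient-safety inconsistency in its own right.

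The time limits raise a lesser question. The 6-week rule speaks of combined cycles, yet Table 7 holds nivolumab alone. If a nivolumab-only hold counts as a delay, a patient could leave the study, and stop contributing later immune and response data, while Table 7 would still allow the hold to continue.

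**Working it through.** The plan states no figure on this point, so the check sets the rules side by side and finds where they give different answers.

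**Step 1: recovery grade.** Inputs: the body text of 10.4.3 (below grade 1) and footnote a (grade 1 or lower).

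| Residual toxicity | Body text of 10.4.3 | Footnote a | Agree? |
|---|---|---|---|
| None | may restart | resume | yes |
| Grade 1 | not allowed | resume | **no** |
| Grade 2 or higher | not allowed | not allowed | yes |

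The texts differ at residual Grade 1 only. The immediate effect there is restart versus continued hold.

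**Step 2: how much of Table 7 is involved.** The rows that withhold a dose are colitis, pneumonitis, hepatitis, hypophysitis, adrenal insufficiency, type 1 diabetes, nephritis, rash, encephalitis, and the first occurrence of another Grade 3 reaction. All ten carry footnote a, so the conflict reaches every hold the table prescribes. The persistent-reaction row covers Grades 2 and 3 only, so it never ends a hold kept open for residual Grade 1 toxicity.

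**Step 3: what the time rules measure.**
- 6-week rule (10.1, 10.2): the trigger is a delay of decitabine/nivolumab cycles; the consequence is leaving the study.
- 12-week rows (Table 7): the trigger is how long a reaction or a steroid requirement lasts; the consequence is stopping nivolumab.

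**Step 4: where the time rules could meet.** Section 10.1 states "For the purposes of this study, 1 cycle = 28 days", and footnote a ties resumption to the next cycle. Ignoring the ±7-day window:
- A hold starting on Day 1 can end at week 4, 8 or 12.
- A hold starting on Day 15 (cycles 1–4) can end at week 2, 6 or 10.

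Restarts that fall after week 6 and before week 12 are those at weeks 8 and 10. There are two readings:
- *A nivolumab-only hold counts as a delay, or decitabine is held as well.* The patient is already off study under 10.1 or 10.2 before a restart at week 8 or 10, and before a 12-week row can apply to the hold.
- *Decitabine stays on schedule and no cycle is delayed.* The 6-week rule is not triggered, and the two sets of rules coexist.

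No section chooses between these readings.

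**Step 5: reach into the primary endpoint.** Section 10.3 defines DLTs as related non-hematologic Grade 4 or 5 toxicities, with an initial period of 28 days after the first decitabine dose. A Cycle 1 Day 15 hold that resumes with the next cycle restarts on Day 29 (28 + 1), after that period. Grade 4 reactions lead to permanent discontinuation under Table 7, so they raise no restart question. On that 28-day period, the DLT proportion in 19.1 is not materially affected; the descriptive safety data are.

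**The case against.** **On the grade.** The mismatch concerns a single residual grade. The body sentence is permissive, and it stands next to a pointer to Table 7, whose modifications are only recommended. An equality sign may have been lost when the PDF was read, although the footnote's sign was read correctly. The Appendix H algorithms are figures that cannot be seen here and may contain restart guidance. All of this is fair, and it limits the weight of the point. It does not remove it: neither the permissive wording nor the pointer tells a site which grade applies, and guidance in an appendix would still leave two conditions within 10.4.3.

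**On the time limits.** A reader might infer that 6 weeks and 12 weeks contradict each other, so that the same patient is retreated under one rule and removed under the other. The documents do not support that as stated. The triggers and consequences differ, and the rules clash only if a nivolumab-only hold is a delay. Some text favours treating the drugs separately: section 10.1 lets a patient elect to stop nivolumab with no cycle limit, and 10.1.2 speaks of nivolumab from cycle 5 only if it is continued. Other text points the other way: the title of Table 7 uses the language of dosing delays for nivolumab, 9.1 provides for continuing on decitabine alone by patient choice after Cycle 8, and 10.6 does not list decitabine alone among the treatments of patients remaining on study. What stands is an open question of scope.

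**On size.** A reader might also take the relapsed AML study described in section 2.3.2, where 15 patients (23%) had immune toxicity and 13 were retreated, and compute 0.23 × 18 = 4.1 patients and 4.1 × 13/15 = 3.6 restarts. Even if those rates carried over from a different population and a different hypomethylating agent, this counts all rechallenges. The study as described does not report how many restarted at residual Grade 1 or after a hold of 6 to 12 weeks. Nor can the disputed 6 weeks be put at three doses in general: 6/2 = 3 holds only in cycles 1–4, and from cycle 5 dosing is every 4 weeks (6/4 = 1.5, so one or two doses).

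**On detection.** At most two sites take part, and all patients are reviewed at least every 2 weeks (section 6). This makes unnoticed divergence less likely, but the review has no single rule to check against.

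**Conclusion.** The recovery-grade contradiction stands as printed: section 10.4.3 gives opposite instructions for residual Grade 1 toxicity, and it does so for every hold in Table 7. It bears on nivolumab exposure and on the descriptive safety data after rechallenge. The number of patients affected cannot be derived from the documents. The conclusion assumes that the inequality sign in the body text appears in the source as it was read.

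The 6-week and 12-week limits are unreconciled but not contradictory. Removal from study does not follow from the grade conflict alone; it needs the further assumption that nivolumab held alone counts as a delay, which the documents leave open.

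Overall this is a modest inconsistency in a restart rule. It should be corrected because it concerns re-exposure after toxicity and is easy to resolve.

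**What to change.** 1. Check the inequality sign in the source document, then reconcile the body sentence of 10.4.3 with footnote a to Table 7 so that a single recovery grade applies.
2. State in 10.1 and 10.2 whether the 6-week limit covers nivolumab held alone while decitabine continues on schedule, and how that limit relates to the two 12-week rows of Table 7.
3. Until this is done, it would help to record for each hold its start date, the residual grade at restart and the rule applied, so that the safety description can be interpreted.

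Which grade and which duration apply is for the sponsor's clinicians. Items 1 and 2 cost only protocol wording in three sections, with no effect on sample size or visits. Item 3 adds a small amount of data entry per hold.

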10.4.3.1 Guidelines on Myocarditis attributed to Nivolumab

For all cardiac safety marker elevations (troponin, CK-MB, BNP), whether in isolation or in combination, nivolumab will be held until investigations can exclude nivolumab. Consult cardiology immediately. If there is high clinical suspicion for nivolumab-induced myocarditis, high-dose steroids (1 gram IV methylprednisolone or equivalent) must be started during hospitalization regardless of availability of cardiac MRI or echocardiogram findings.

If patient is asymptomatic/at baseline but there is new isolated BNP elevation, obtain echocardiogram immediately. Daily clinic assessment including cardiac biomarkers should be performed if patient's symptoms are unchanged from baseline, echocardiogram normal or baseline, additional safety markers and vital signs remain normal. If patient has new symptoms e.g. weakness, fatigue, dyspnea, edema, etc. regardless of severity accompanied by isolated BNP elevation, cardiac MRI must be obtained as soon as possible regardless of echocardiogram findings. Hospital admission for cardiac monitoring must be considered along with institution of supportive medications.

PROTOCOL TITLE: I 49217 - Phase 1 CDX-1401/ Poly-ICLC +Decitabine +Nivolumab in Patients with MDS or Low Blast Count AML

If patient is asymptomatic/at baseline with normal renal function but troponin rises to greater than 0.10, investigate for the presence of acute pulmonary embolism and acute coronary syndrome in addition to guidelines above.

Hold treatment if patient is asymptomatic but new persistent ECG changes noted on triplicate readings along with normal troponin, CK-MB, BNP and echocardiogram. Consult cardiology. Repeat ECG and labs no earlier than 12 hours later. If ECG changes are transient, may continue treatment.

For documented echocardiographic changes regardless of cardiac safety marker levels, cardiac MRI must be obtained. Hold study treatment. If treatment-induced myocarditis is suspected, high-dose steroids must be instituted as detailed above.

10.5 General Concomitant Medication and Supportive Care

Subjects will receive standard pre-treatment with anti-emetics prior to decitabine administration. Subjects may be treated for breakthrough nausea and vomiting with appropriate anti-emetics.

The use of all standard supportive medication is permitted, although concurrent treatment with immunosuppressive or immunomodulatory agents is strongly discouraged. Concomitant systemic corticosteroids are to be avoided if at all possible. If used, doses of steroids should be the minimum necessary for appropriate clinical management. If clinically necessary, topical or systemic non-steroidal anti-inflammatory or antihistamines may be used as alternatives.

Subjects should not be receiving concomitant long-term corticosteroids at a dose greater than 15 mg of prednisone equivalents. The use of corticosteroids for management of nausea, osteoarthritis gout, or other symptoms at doses less than 15 mg of prednisone equivalents is permitted.

The Investigator may, at his/her discretion, arrange for a patient to have an unscheduled visit, especially in the case of AEs that require follow-up. If a patient is experiencing an AE considered by the Investigator to be possibly related to the study drug, an unscheduled visit should be performed; the unscheduled visit pages for the eCRF must be completed.

